4.4 Safety measurements

Please refer to the study plans in Table 1 through Table 3 for the precise timing of safety measurements.

4.4.1 Demographics and informed consent

The patient's signed and dated informed consent form must be obtained before conducting any procedure specifically for the study (Refer to Section 7.3). Demographics (date of birth, sex, race, date of signed informed consent) for each patient will be obtained and collected on the appropriate CRF, whether or not they are entered into the study.

4.4.2 Inclusion and exclusion criteria

The inclusion and exclusion criteria must be assessed and reviewed with each patient at the screening visit, Day -1 of Periods I and II in order to establish and confirm their eligibility to participate in the study.

4.4.3 Medical history

A detailed medical history including surgical and medication histories will be recorded for each patient at the initial screening visit and updated at admission on Day -1 of Periods I and II. Significant medical conditions that have occurred within the past 2 years or conditions that are ongoing (ie, headache, backache, indigestion) are to be recorded in the appropriate pCRF.

The medication history must identify any known drug allergies, presence or history of drug abuse and use of chronic medications. All medications and over-the-counter (OTC) products (including vitamins and herbal products) taken within 2 weeks before Day -1 of Period I are to be recorded on the pCRF.

4.4.4 Laboratory safety measurements

Blood and urine samples for determination of clinical chemistry, hematology and urinalysis parameters will be taken at the times given in the study plan (Table 1). The date and time of collection will be recorded on the appropriate pCRF.

The following laboratory variables will be measured:

Periods I and II

Clinical chemistry	Hematology	Urinalysis	
Calcium	Hemoglobin	Specific gravity	
Glucose	Hematocrit	РН	
Total bilirubin	Erythrocytes (RBCs)	Glucose	
Alkaline phosphatase	Leukocytes (WBCs)	Ketones	
Creatinine	Platelet count	Protein	
Total protein	Red cell distribution width	Bilirubin	
Albumin	Mean corpuscular volume	Occult blood	
Aspartate aminotransferase	Mean corpuscular hemoglobin concentration (MCHC)	Microscopic analysis of formed elements ^a	
Alanine aminotransferase	Differential leukocytes including:		
Sodium	Lymphocytes		
Potassium	Basophils		
Magnesium	Monocytes		
Phosphate	Neutrophils		
Blood urea nitrogen	Eosinophils		
Chloride			
Uric acid			
Gamma glutamyl transferase			
Creatine kinase (CK)			

1.

m. ^aIf a urine sample is positive for protein or blood, a microscopic examination of the urine sediment will be performed.

If any of the tests performed on the samples taken after investigational product administration show clinically abnormal results as judged by the investigator, new blood samples will be taken and repeated until the results return to baseline or the cause is assessed. The investigator will provide an evaluation of the clinical importance of the deviation. The development of any clinically relevant deterioration in any laboratory test may constitute an AE if it leads to discontinuation of the study drug or if it fulfills the criteria of seriousness.

If ALT, AST, or bilirubin elevations are $\ge 3 \times ULN$ at any time, AstraZeneca should be informed immediately.

4.4.5 Urine drug screen

Urine will be tested for the following drugs of abuse: benzodiazepines, cocaine and/or metabolites, amphetamines, tetrahydrocannabinol (THC), opiates, phencyclidine (PCP), and barbiturates.

If a patient tests positive for drugs of abuse they will be excluded from entering, or continuing in, the study. If the drug is illegal, advice will be offered and the patient will be removed from the AstraZeneca Volunteer Panel.

4.4.6 HIV and hepatitis screens

Testing for the HIV antibody, HBsAg, and Hepatitis C antibody is to be performed on all patients at screening only. If a test result is positive, the patient will not be allowed to proceed in the study.

Note: Although the results of the HIV and hepatitis screens must be documented in the patient's files, they will not be collected on the pCRFs and will therefore not be recorded in the study database.

4.4.7 Breath ethanol testing

Breath ethanol will be measured at the times specified in Table 1 and Table 2 If the result is positive, the patient will not be permitted to proceed in the study.

4.4.8 Serum pregnancy test

All women will have a serum β -HCG test at the times specified in Table 1 and Table 2. If at any point at pregnancy test result is positive, the patient will not be allowed to proceed in the study.

Serum pregnancy tests may be run on the same blood collected fro the serum chemistry analysis, Refer to Section 8.4 for instructions regarding the reporting and follow-up of pregnancies. No study medication may be given to a woman who has not had negative results on the initial serum pregnancy test as well as the subsequent serum pregnancy tests. The results of the pregnancy tests will be recorded on the CRF as "positive" or "negative".

4.4.9 Electrocardiographic measurements

For timing of individual measurements refer to study plans Table 1 and Table 2.

4.4.9.1 Resting 12-lead ECG

Twelve-lead ECGs will be obtained after the patient has been lying down for 5 minutes in each case. The following ECG results will not be collected on the pCRFs unless a clinically significant result is obtained: Study Day 4 pre dose, pre and post cycle exercise test. If a clinically significant result occurs, the result will be recorded as an adverse event.

4.4.9.2 Telemetry

Continuous ECG monitoring will be performed from 15 minutes prior to the first administration of study drug (Day 1) until 24 hours after the last administration of study drug (Day 5) per study period. If there are multiple pauses on the telemetry of 2.5 seconds or greater in ventricular beats caused by sinoatrial arrest or AV block the subject may be discontinued from the trial. If possible, AstraZeneca should be consulted before discontinuing a subject.

4.4.10 Vital signs

Vital signs assessments in addition to those discussed below can be made at the discretion of the investigator in order to follow the patient's clinical condition. These assessments should be entered as unscheduled assessments in the appropriate sections of the pCRF.

4.4.10.1 Blood pressure and heart rate

Blood pressure and heart rate will be measured with an appropriate cuff size after the patient has been sitting for at least 5 minutes. As much as possible, for each patient throughout the study, blood pressure should be measured using the same arm.

For timing of individual measurements refer to Table 1 and Table 2. The following blood pressure and heart rate measurements will not be captured on the pCRFs unless a clinically significant result is obtained. Study Day 1: 3 hour post AM dose; study Days 2, 3 and 4: predose (AM) and 3 hours post AM dose. If a clinically significant result is obtained at this time it will be recorded as an adverse event.

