In Disperse 2, a 12 week study in patients with non-ST elevation acute coronary syndrome, Holter ECG monitor evaluation was conducted in patients for up to 7 days post event (average recording of about 4 days). There were Holter data available for 305 patients on the 90 mg dose of AZD6140, 284 patients on the 180 mg dose of AZD6140, 297 on the 75 mg dose of clopidogrel. At post hoc evaluation of this data demonstrated an increased incidence of the occurrence of pauses, dropped beats, and bradycardia on Holter monitoring in the AZD6140 groups compared to clopidogrel. These Holter observations were not generally associated with symptoms. The frequency of pauses over 2.5 seconds was 17 for the 90 mg of AZD6140, 28 for the 180 mg dose of AZD6140 and 13 for the 75 mg dose of clopidogrel. For dropped beats (>180% RR interval) there were 88 for the 90 mg dose of AZD6140, 89 for the 180 mg dose of AZD6140 and 73 for the 75 mg dose of clopidogrel. The occurrence of bradycardia (4 beats<45 bpm) was 103 for the 90 mg dose of AZD6140, 106 for the 180 mg dose of AZD6140, and 96 for the 75 mg dose of clopidogrel.

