There will be at least a 7 outpatient day washout period between Period I and Period II. b.

- Within 4 to 7 days of Period II (Day 5). c.
- Weight only. d.
- A 12 lead ECG will be performed at screening and should not show any clinically significant abnormalities e. including significant AV block (2nd or 3rd degree).
- f. Telemetry will be performed from 30 minutes prior to the first administration of study drug (Day 1) until 24 hours after the last administration of study drug (Day5).
- Prior to study drug administration Period 1. g.
- h. Patients will be shown the basic assessments at the screening visit to ensure they can comply with the procedures required of the study. A full cardiopulmonary exercise test is not performed at screening, however, patients will be asked to demonstrate that they can utilize the equipment for the test and will be familiarized with the procedure.
- i. Hand-held peak flow meter may be used during nocturnal occurrences of dyspnea, if the spirometry technician is unavailable. A baseline value will be obtained on Day 1 with spirometry testing (Pre-AM dose).
- SAE's will be collected from the time of the informed consent is obtained through the Follow-Up visit. Non 1. SAE's will be collected from the time of the 1st dose on Day 1,Period I through the Follow-Up visit.

Table 2Study Plan Periods I and II

	Period I (Visit 2) and Period II (Visit 3) ^a																					
Study Day	-1			1						2			3					4				5
Study hour relative to dose		PreDose	0	2	3	4	8	12	0	3	12	0	3	12	0	2	3	4	6	8	12	24
Admission/inpatient stay	2	۲																			2	X
Inclusion/exclusion criteria	Х																					
Medical history update	Х																					
Clinical laboratory assessments	Х											Х										X
Brief physical examination	Х																					X
Breath ethanol test	Х																					
Serum pregnancy test (females only)	Х																					
Urine drug screen	Х																					
12-lead ECG ^b	Х														Х				Х			Х
Telemetry ^c		Х	Х	Х	Х	Х	Х	Х	Х	Х	Х	Х	Х	Х	Х	Х	Х	Х	Х	Χ	Х	Х
Oral temperature	Х																					Х
BP and heart rate	Х	Х			Х				Х	Х		Х	Х		Х		Х					Х
Randomization (AZD6140 or placebo) ^d			Х																			
Pharmacogenetic sample ^d		Х																				
AZD6140/placebo administration			Х					Х	Х		Х	Х		Х	Х							
AZD6140/AR-C124910XX PK sample ^e		Х		Х	Х	Х	Х	Х	Х	Х		Х	Х		Х	Х	Х	Х		Χ	Х	Х
Modified Borg Scale /Bidirectional Dyspnea Index		X		X	X	Х	Х	Х	X	Х		X	Х		Х	Х	X	X		Х	Х	X

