Minute ventilation including respiratory rate		Х		X	X	Х	Х	Х	X	Х		X	Х		Х	Х	X	X		X	Х	X

Period I (Visit 2) and Period II (Visit 3) ^a																						
Study Day	-1			1						2			3					4				5
Study hour relative to dose		PreDose	0	2	3	4	8	12	0	3	12	0	3	12	0	2	3	4	6	8	12	24
Spirometry (FEV ₁ , FVC, PEF)	Х	Х			Х			Х	Х	Х		Х	Х		Х		Х				Х	Х
Pulse oximetry		Х		Х	Х	Х	Х	Х	Х	Х		Х	Х		Х	Х	Х	Х		Х	Х	Х
Hand-held peak flow meter ^f		Х																				
Cardiopulmonary exercise test ^g																			Х			
Concomitant medication monitoring	edication monitoring XX																					
Adverse event monitoring	У	ζ																			Y	X
Discharge from study center																						X^h

a. Separated by at least a 7 outpatient day washout period.

b. An ECG will be performed pre and post cycle exercise test on Study Day 4. ECG results obtained on Study Days 4 and 5 will not be collected on the pCRF. Any clinically significant changes will be recorded as an AE.

c. Continuous ECGs (telemetry will be performed from 15 minutes pre-dose until 24 hours after the last dose (Day 5) per study period).

d. Prior to dose administration on Study Day 1 of Period I only.

e. If a PK sample and dose administration are scheduled at the same time, the PK sample should be obtained just prior to dose administration are scheduled at the same time.

f. Hand-held peak flow meter may be used during nocturnal occurrences of dyspnea, if spirometry technician unavailable. A baseline value will be obtained predose on Study Day 1 with spirometry testing.

g. Cardiopulmonary exercise will be performed from 5-7 hours post dose.

h. After completion of all study related procedures.

Table 3	Procedures for	r Spontaneous	Dyspnea Episode	,
	110000010510	Spontaneous	Dyspinca Episoue	-

Period I (Visit 2) and Period II (Visit 3)						
Procedure ^a	Sequence					
Modified Borg Scale/Bidirectional Dyspnea Index	1					
Pulse oximetry	2					
Minute ventilation including respiratory rate	3					
Spirometry (FEV ₁ , FVC, PEF) ^b	4					
AZD6140/AR-C124910XX PK sample	5					

a. The first time a patient reports experiencing dyspnea, and for subsequent episodes thereafter, these procedures are to be completed sequentially. Additionally, at the investigator's discretion, other diagnostic tests such as an ABG, echocardiography, chest x-ray and auscultation over the chest and trachea may be performed to evaluate dyspnea

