4.7.1.2 Recording of adverse events

The patients will be told to report any AE occurring during the study to the investigator or his personnel. Open standardized AE questioning, such as "Have you had any health problems since the previous visit?" will be done by the investigators or their personnel at each contact with the patient. The AE open standardized questioning should be done discretely in order to prevent the patients from influencing each other.

Any AEs observed or reported by a patient and/or staff, will be recorded in the CRF. Any AE including clinical findings not resolved at the follow-up visit, will be followed up at an additional visit or telephone contact within 7 days after the follow-up visit or until resolved or explained.

Laboratory and vital sign abnormalities will not be recorded as an AE unless any criterion for an SAE is fulfilled, the patient discontinues the study due to the result(s), or the investigator insists that it should be reported as an AE. If a laboratory value or vital sign is associated with clinical signs and symptoms, the signs and symptoms should be reported as an AE and the associated laboratory or vital signs should be considered additional information. Any sign or symptom that fulfills the SAE definition (Appendix B) or is the reason for discontinuation of treatment of investigational products should be reported accordingly.

The following variables will be recorded for each AE noted:

- Onset, resolution
- Intensity (mild/ moderate/ severe)
- Action(s) taken
- Outcome of the AE
- Causality of the AE (yes or no)
- Whether it constitutes an SAE or not

The intensity rating is defined as:

- 1 = mild (awareness of sign or symptom, but easily tolerated)
- 2 = moderate (discomfort sufficient to cause interference with normal activities)
- 3 = severe (incapacitating, with inability to perform normal activities)

It is important to distinguish between serious and severe AEs. Severity is a measure of intensity whereas seriousness is defined by the criteria in Section 4.7.1.1. An AE of severe intensity need not necessarily be considered serious. For example, nausea that persists for several hours may be considered severe nausea, but not a SAE. On the other hand, a stroke that results in only a limited degree of disability may be considered a mild stroke but would be a SAE.

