6.4.3.4 Safety

Safety data (adverse events, vital signs, 12-lead ECGs, physical examination data, laboratory data) will be summarized at each scheduled time point by treatment using descriptive statistics.

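### The resting blood pressure, heart rate and 12-lead ECG values taken on dosing days are kept off the pCRF, so the promised safety summary cannot be produced for those time points

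*Combined protocol and SAP*

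**What the plan says.** **BP/HR.** Table 2 schedules resting readings on Day -1, on Day 1 predose and at 3 h, at 0 h and 3 h on each of Days 2, 3 and 4, and on Day 5 at 24 h. Section 4.4.10.1 then says: "The following blood pressure and heart rate measurements will not be captured on the pCRFs unless a clinically significant result is obtained". The readings concerned are: "Study Day 1: 3 hour post AM dose; study Days 2, 3 and 4: predose (AM) and 3 hours post AM dose". A clinically significant result is to be entered as an adverse event (AE).

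**12-lead ECG.** Table 2 schedules ECGs on Day -1, Day 4 and Day 5, with the Day 4 recordings made predose and before and after the exercise test. Footnote b to Table 2 says: "ECG results obtained on Study Days 4 and 5 will not be collected on the pCRF". Section 4.4.9.1 is narrower: "The following ECG results will not be collected on the pCRFs unless a clinically significant result is obtained: Study Day 4 pre dose", followed by the two recordings around the exercise test. It does not mention Day 5. Both places send clinically significant findings to the AE record.

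**Planned use.** Section 6.2.1 promises changes from baseline for vital signs and 12-lead ECGs. Section 6.4.3.4 says: "Safety data (adverse events, vital signs, 12-lead ECGs, physical examination data, laboratory data) will be summarized at each scheduled time point by treatment". The synopsis adds that this is done for each of the two cohorts.

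**AE rule.** Section 4.7.1.2 says: "Laboratory and vital sign abnormalities will not be recorded as an AE unless any criterion for an SAE is fulfilled", with two further exceptions: the patient discontinues because of the result, or the investigator insists on reporting it.

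**Background.** Section 1.1 reports that a post hoc evaluation in an earlier acute coronary syndrome study "demonstrated an increased incidence of the occurrence of pauses, dropped beats, and bradycardia on Holter monitoring in the AZD6140 groups compared to clopidogrel".

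**The concern.** The data-capture rules and the analysis promises do not fit together. A descriptive summary at a time point needs every patient's value at that time point. Here the ordinary values on the dosing days are measured and then left out of the database, and only those judged clinically significant come through, as AEs. That is selective capture: means, ranges and changes from baseline cannot be built from it.

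The withheld readings are also the ones closest to peak exposure. Section 1.1 puts the time to peak at 1.5 to 3 h, and all four 3 h BP/HR readings (Days 1 to 4, including the one after the 450 mg dose) are on the withheld list.

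What is at stake is the secondary objective on safety and tolerability. A crossover against placebo is well suited to showing a modest within-patient shift in resting heart rate or blood pressure, but the readings that would show it during dosing are not retained.

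**Working it through.** The plan gives no figure to reproduce, so the check is a count of Table 2 against the exclusion lists.

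**Step 1: BP/HR per period.** Inputs are the Table 2 row labelled "BP and heart rate" and the list in 4.4.10.1.

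| Time point | Withheld by 4.4.10.1? |
|---|---|
| Day -1 | No |
| Day 1 predose | No |
| Day 1, 3 h | Yes |
| Day 2, predose and 3 h | Yes (2) |
| Day 3, predose and 3 h | Yes (2) |
| Day 4, predose and 3 h | Yes (2) |
| Day 5, 24 h | No |

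- Scheduled: 10. Withheld: 1 + 2 + 2 + 2 = 7, which is 7/10 = 70%.
- After the first dose through Day 4: 7 scheduled, 7 withheld.
- After the first dose within the period, counting Day 5: 8 scheduled, 7 withheld (7/8 = 88%).

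**Step 2: ECG per period.**

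| Recording | Table 2 footnote b | Section 4.4.9.1 |
|---|---|---|
| Day -1 | Kept | Kept |
| Day 4 predose | Withheld | Withheld |
| Day 4 before exercise | Withheld | Withheld |
| Day 4 after exercise | Withheld | Withheld |
| Day 5 | Withheld | Not listed, so kept |

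Under either text no dosing-day ECG is routinely collected. Whether an in-period post-dose ECG survives depends on which text governs Day 5.

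**Step 3: what the Day 5 reading can show.** Section 1.1 gives a mean half-life of 6 to 13 h. Assuming simple exponential decline, the fraction left 24 h after the last dose is 0.5^(24/t½):

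- t½ = 6 h: 0.5^4 = 0.06
- t½ = 13 h: 0.5^(24/13) = 0.28

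So the one retained in-period post-dose BP/HR reading reflects roughly 6% to 28% of the earlier level. That is low, but not necessarily zero.

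**Step 4: number of values involved.**

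- BP/HR: 7 readings × 2 periods × 24 patients = 336 (× 16 completers = 224).
- ECG: up to 4 recordings × 2 periods × 24 patients = 192. The factor 4 counts Day 5 as withheld.

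**Step 5: is there another route into the database?** Section 5.7.1 says the pCRF holds whatever is not captured electronically. No electronic capture of these readings is described.

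**The case against.** Several points on the other side stand and limit the finding.

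- **Some values remain.** Day 5 BP/HR is captured in both periods, so a Day 1 predose to Day 5 change by treatment can be summarised. BP/HR and ECG at follow-up (Table 1, section 4.1.2) carry no exclusion. Section 4.4.10 puts unscheduled vital signs on the pCRF. A reader might infer that every on-treatment value is lost and that no safety summary is possible; the documents do not support that.
- **Exercise-test data.** Section 4.3.7.4 records heart rate and blood pressure on the pCRF during loadless pedalling, exercise and recovery. The test takes place on Day 4, 5 to 7 h after the dose, in both periods. These are not seated resting values, but they are numeric comparisons of drug with placebo within patients. It would therefore be wrong to say that a shift could not be seen at all.
- **The pause signal.** It is tempting to say that the plan is blind to the pauses and bradycardia described in section 1.1. That signal came from Holter monitoring, and the matching instrument here is continuous telemetry (section 4.4.9.2), not seven cuff readings. Turning the Holter counts into percentages would assume that they are patients, which section 1.1 does not say. What stands is narrower: telemetry is a listed safety variable in the synopsis, yet 6.2.1 and 6.4.3.4 omit it. Section 6.4.1 defers detail to an analysis plan still to be written, so the omission can be asserted only of the protocol text.
- **AE recording.** Sections 4.4.10.1 and 4.7.1.2 look contradictory but can be applied together, because the investigator may insist on reporting a value. They still need to be aligned.
- **A cheaper cure.** Narrowing 6.4.3.4 to the captured time points would remove the inconsistency. It would not supply the missing dosing-day values.

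**Conclusion.** The mismatch is real. In each period all 7 scheduled resting BP/HR readings from after the first dose through Day 4, and all Day 4 12-lead ECGs, are measured but kept off the pCRF unless judged clinically significant. The Day 5 ECG is excluded by Table 2 footnote b and not by 4.4.9.1. The changes from baseline and by-time-point summaries promised in 6.2.1 and 6.4.3.4 cannot be produced for those time points, so the safety summary is incomplete.

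This rests on reading the exclusion lists literally and on there being no electronic capture outside the documents. The half-life calculation is supporting context only.

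It should be fixed, but it does not threaten the trial's main purpose. A secondary safety objective is affected; respiratory rate and minute ventilation are not. The study is exploratory, with no power calculation and no formal safety analysis.

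**What to change.** 1. Delete the sentences that withhold results in 4.4.9.1, 4.4.10.1 and Table 2 footnote b, and record every scheduled resting BP/HR and 12-lead ECG result on the pCRF. This also settles the Day 5 ECG conflict.
2. Add telemetry findings by treatment to the summaries in 6.4.3.4.
3. Reconcile 4.4.10.1 with 4.7.1.2 on when an abnormal vital sign is recorded as an AE.

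The cost is data entry: at most 336 BP/HR records and 192 ECG records if all 24 patients complete both periods, plus tabulation of telemetry already being collected. No procedure, visit or patient burden is added. The change is best made before database lock, since values never entered may be hard to recover afterwards.
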